8.1.2 Sera / Plasma for Banking

Sera, plasma and red blood cells will be acquired and banked for possible exploratory studies for future testing to investigate toxicities or treatment outcomes.

8.1.3 Archival Tissue

If tissue is available and the patient has signed consent, samples will be submitted to Caris Life Sciences® for mutational studies and additional biomarker analysis.

T 25-30 (4-5 μ m) unstained sections placed on positively charged slides will be prepared and sent to Caris Life Sciences® under the patient's name for testing. Results will be returned for placement into the patient's medical records, clinical trial record and to the attending physician. Caris will provide data under the patient study number for informatics manipulation to be performed at Fox Chase Cancer Center.

If a biopsy is performed on the patient as standard of care, and the patient has signed consent, and if sufficient tumor tissue is collected, the tumor biopsy, in addition or in place of archival tissue, will be submitted to Caris as described above.

Correlative Special Studies.

Sample requirements:

Timepoints	PK (Quinacrine/	Sera/Plasma for	Tissue ++
_	Capecitabine)	banking	(Archival or Biopsy)
Prior to treatment			25-30 (4-5µm)
Screening (Day -14 to -1)			unstained slides
Cycle 1 Day 1 Pre 0hr	1(4mL) Li heparin	1(5mL) red top	
	1(4mL) EDTA	1(4mL) EDTA#	
1hr post dose	1(4mL) Li heparin		
	1(4mL) EDTA		
2hr post dose	1(4mL) Li heparin		
	1(4mL) EDTA		
4hr post dose	1(4mL) Li heparin		
	1(4mL) EDTA		
8hr post dose	1(4mL) Li heparin		
	1(4mL) EDTA		
Cycle 2 Day 1 Pre 0hr	1(4mL) Li heparin		
	1(4mL) EDTA		
Cycle 3 Day 1 Pre 0hr	1(4mL) Li heparin		
	1(4mL) EDTA		

And at end of treatment or at progression, whichever comes first.

++ If archival tissue is available, or if a standard of care biopsy is being performed

8.2 Collection of Specimens

Blood samples will be drawn at the same time as other blood for routine clinical tests. All samples will be processed, stored, and/or distributed by the Protocol Support Laboratory at Fox Chase Cancer Center. The Protocol Support Laboratory will be responsible for labeling of all specimens with the patient assigned study number only.

No additional tests or samples for the study will be requested following the final cycle of chemotherapy.

9. STUDY CALENDAR

Baseline evaluations are to be conducted within 14 days prior to administration of protocol therapy. Scans and x-rays must be done \leq 4 weeks prior to the start of therapy. In the event that the patient's condition is deteriorating, laboratory evaluations should be repeated within 48 hours prior to initiation of the next cycle of therapy.

	PRE-TX	C 1	C 2	C 3	C 4	C 5	C 6	C 7	C 8	C 9	C 10	C 11	C12-18	End of Treatment	Follow Up ^f
Quinacrine (Days 1-21 of		х	х	х	х	х	х	х	х	х	х	х	х		
each cycle)															
Capecitabine (Days 1-14 of each cycle)		х	х	х	х	х	х	х	х	х	х	х	х		
Informed consent	Х														
Demographics	Х														
Medical history	х														
Concurrent meds	Х	X											Х		
Physical exam	х	Х	Х	Х	Х	Х	Х	Х	Х	Х	х	х	Х	Х	
Vital signs ^c	Х	Х	Х	Х	Х	Х	Х	Х	Х	Х	Х	Х	Х	Х	
Height	Х														
Weight	х	Х	Х	Х	Х	Х	Х	Х	Х	Х	Х	х	Х	Х	
ECOG P/S	х	Х	Х	Х	Х	Х	Х	Х	Х	Х	Х	х	Х	Х	
CBC w/diff, plts	Х	х	х	Х	х	Х	Х	Х	Х	Х	х	х	Х	х	
Serum chemistry ^a	Х	Х	Х	Х	Х	Х	Х	Х	Х	Х	Х	Х	Х	Х	
EKG (as indicated)	х														
CEA & CA 19-9 ^k	х	Х	х	Х	Х	Х	Х	Х	Х	Х	х	х	х		
AE evaluation		Х											Х	Х	
Radiologic evaluation	x	Radiologic measurements should be performed after every 3 cycles. DocumentationX(radiologic) must be provided for patients removed from study for progressive disease										mentation sive disease.	X e		
B-HCG	Xp														
PKs Phase I & II		х	х	х											
Tissue Collection		x ^j													
Sera/Plasma banking		x ⁱ												x	
Overall Survival															x ^d
a:Albumin, alkaline phosph phosphorus, potassium, tot b:Serum pregnancy test (w c:Vital Signs: Heart Rate, Bl d:Telephone call is appropr e:Every 6 or 9 weeks per pr f: Until death, lost to follow I: Sera/Plasma for banking J: If archival tissue is availal Caris Life Sciences® for eva K: CEA and CA 19-9 are to b C = cycle # and day 1 of tha	atase, t al prote omen o ood Pre rate if p rotocol u up or c C1D1 p ble (or if luation. be perfo it cycle.	otal b in, SG f child ssure atien until c off stu re and f a sta	oilirub GOT[A dbear c, Resp t is ur diseas udy du d end andaro	in, bid ST], S ing po piratio nable e pro ue to s of tre d of ca ay on	carbo GPT[/ otenti ons, T to be gressi 5 year eatme are bi e of e	nate, ALT], s al) to empe seen on. cs pas ent opsy i very	BUN, sodiu be pe ratur in clir sing f is per cycle	calciu m. erforn e. nic. rom t forme	ım, ch ned w he rei ed) un	nlorid rithin mova ostaine	e, creati 72 hour I of ther ed slide	inine, glu rs of beg rapy s will be	ucose, LDH, inning thera prepared fo	apy or submission	n to

10. MEASUREMENT OF ANTITUMOR EFFECT

Page 32 of 50

For the purposes of this study, patients should be re-evaluated for response after every 3 cycles. In addition to a baseline scan, confirmatory scans should also be obtained 6 weeks following initial documentation of objective response.

Response and progression will be evaluated in this study using the revised Response Evaluation Criteria in Solid Tumors (RECIST) guideline (version 1.1). Changes in the largest diameter (unidimensional measurement) of the tumor lesions and the shortest diameter in the case of malignant lymph nodes are used in the RECIST criteria.

Definitions

Evaluable for toxicity: All patients will be evaluable for toxicity from the time of their first treatment with quinacrine in combination with capecitabine. During the course of treatment, patients will be evaluated according to the National Cancer Institute CTCAE (current version 4.0).

Evaluable for objective response: Only those patients who have measurable disease present at baseline, have received at least one cycle of therapy, and have had their disease re-evaluated will be considered evaluable for response. These patients will have their response classified according to the definitions stated below. (Note: Patients who exhibit objective disease progression prior to the end of cycle 1 will also be considered evaluable.)

Evaluable Non-Target Disease Response: Patients who have lesions present at baseline that are evaluable but do not meet the definitions of measurable disease, have received at least one cycle of therapy, and have had their disease re- evaluated will be considered evaluable for non-target disease. The response assessment is based on the presence, absence, or unequivocal progression of the lesions.

Disease Parameters

Measurable disease: Measurable lesions are defined as those that can be accurately measured in at least one dimension (longest diameter for non-nodal lesions and short axis for nodal lesions to be recorded) as >20 mm by chest x-ray, as >10 mm with CT scan, or >10 mm with calipers by clinical exam. All tumor measurements must be recorded in millimeters (or decimal fractions of centimeters). Note: Tumor lesions that are situated in a previously irradiated area might or might not be considered measurable. If the investigator thinks it appropriate to include them, the conditions under which such lesions should be considered must be defined in the protocol.

Malignant lymph nodes: To be considered pathologically enlarged and measurable, a lymph node must be >15 mm in short axis when assessed by CT scan (CT scan slice thickness recommended to be no greater than 5 mm). At baseline and in follow-up, only the short axis will be measured and followed.

Non-measurable disease: All other lesions (or sites of disease), including small lesions (longest diameter <10 mm or pathological lymph nodes with \geq 10 to < 15 mm short axis), are considered non-measurable disease. Bone lesions, leptomeningeal disease, ascites, pleural/pericardial effusions, lymphangitis cutis/pulmonitis, inflammatory breast disease, and abdominal masses (not followed by CT or MRI), are considered as non-measurable.

Note: Cystic lesions that meet the criteria for radiographically defined simple cysts should not be considered as malignant lesions (neither measurable nor non- measurable) since they are, by definition, simple cysts.

'Cystic lesions' thought to represent cystic metastases can be considered as measurable lesions, if they meet the definition of measurability described above. However, if non-cystic lesions are present in the same patient, these are preferred for selection as target lesions.

Target lesions: All measurable lesions up to a maximum of 2 lesions per organ and 5 lesions in total, representative of all involved organs, should be identified as target lesions and recorded and measured at baseline. Target lesions should be selected on the basis of their size (lesions with the longest diameter), be representative of all involved organs, but in addition should be those that lend themselves to reproducible repeated measurements. It may be the case that, on occasion, the largest lesion does not lend itself to reproducible measurement in which circumstance the next largest lesion which can be measured reproducibly should be selected. A sum of the diameters (longest for non-nodal lesions, short axis for nodal lesions) for all target lesions will be calculated and reported as the baseline sum diameters. If lymph nodes are to be included in the sum, then only the short axis is added into the sum. The baseline sum diameters will be used as reference to further characterize any objective tumor regression in the measurable dimension of the disease.

Non-target lesions: All other lesions (or sites of disease) including any measurable lesions over and above the 5 target lesions should be identified as non-target lesions and should also be recorded at baseline. Measurements of these lesions are not required, but the presence, absence, or in rare cases unequivocal progression of each should be noted throughout follow-up.

Methods for Evaluation of Measurable Disease

All measurements should be taken and recorded in metric notation using a ruler or calipers. All baseline evaluations should be performed as closely as possible to the beginning of treatment and never more than 4 weeks before the beginning of the treatment.

The same method of assessment and the same technique should be used to characterize each identified and reported lesion at baseline and during follow-up. Imaging-based evaluation is preferred to evaluation by clinical examination unless the lesion(s) being followed cannot be imaged but are assessable by clinical exam.

Clinical lesions: Clinical lesions will only be considered measurable when they are superficial (e.g., skin nodules and palpable lymph nodes) and ≥ 10 mm diameter as assessed using calipers (e.g., skin nodules). In the case of skin lesions, documentation by color photography, including a ruler to estimate the size of the lesion, is recommended.

Chest x-ray: Lesions on chest x-ray are acceptable as measurable lesions when they are clearly defined and surrounded by aerated lung. However, CT is preferable.

Conventional CT and MRI: This guideline has defined measurability of lesions on CT scan based on the assumption that CT slice thickness is 5 mm or less. If CT scans have slice thickness greater than 5 mm, the minimum size for a measurable lesion should be twice the slice thickness. MRI is also acceptable in certain situations (e.g. for body scans).

Use of MRI remains a complex issue. MRI has excellent contrast, spatial, and temporal resolution; however, there are many image acquisition variables involved in MRI, which greatly impact image

quality, lesion conspicuity, and measurement. Furthermore, the availability of MRI is variable globally. As with CT, if an MRI is performed, the technical specifications of the scanning sequences used should be optimized for the evaluation of the type and site of disease. Furthermore, as with CT, the modality used at follow-up should be the same as was used at baseline and the lesions should be measured/assessed on the same pulse sequence. It is beyond the scope of the RECIST guidelines to prescribe specific MRI pulse sequence parameters for all scanners, body parts, and diseases. Ideally, the same type of scanner should be used and the image acquisition protocol should be followed as closely as possible to prior scans. Body scans should be performed with breath-hold scanning techniques, if possible.

PET-CT: At present, the low dose or attenuation correction CT portion of a combined PET-CT is not always of optimal diagnostic CT quality for use with RECIST measurements. However, if the site can document that the CT performed as part of a PET-CT is of identical diagnostic quality to a diagnostic CT (with IV and oral contrast), then the CT portion of the PET-CT can be used for RECIST measurements and can be used interchangeably with conventional CT in accurately measuring cancer lesions over time. Note, however, that the PET portion of the CT introduces additional data which may bias an investigator if it is not routinely or serially performed.

Ultrasound: Ultrasound is not useful in assessment of lesion size and should not be used as a method of measurement. Ultrasound examinations cannot be reproduced in their entirety for independent review at a later date and, because they are operator dependent, it cannot be guaranteed that the same technique and measurements will be taken from one assessment to the next. If new lesions are identified by ultrasound in the course of the study, confirmation by CT or MRI is advised. If there is concern about radiation exposure at CT, MRI may be used instead of CT in selected instances.

Endoscopy, Laparoscopy: The utilization of these techniques for objective tumor evaluation is not advised. However, such techniques may be useful to confirm complete pathological response when biopsies are obtained or to determine relapse in trials where recurrence following complete response (CR) or surgical resection is an endpoint.

Tumor markers: Tumor markers alone cannot be used to assess response. If markers are initially above the upper normal limit, they must normalize for a patient to be considered in complete clinical response.

Cytology, Histology: These techniques can be used to differentiate between partial responses (PR) and complete responses (CR) in rare cases (e.g., residual lesions in tumor types, such as germ cell tumors, where known residual benign tumors can remain).

The cytological confirmation of the neoplastic origin of any effusion that appears or worsens during treatment when the measurable tumor has met criteria for response or stable disease is mandatory to differentiate between response or stable disease (an effusion may be a side effect of the treatment) and progressive disease.

FDG-PET: While FDG-PET response assessments need additional study, it is sometimes reasonable to incorporate the use of FDG-PET scanning to complement CT scanning in assessment of progression (particularly possible 'new' disease). New lesions on the basis of FDG-PET imaging can be identified according to the following algorithm:

- a. Negative FDG-PET at baseline, with a positive FDG-PET at follow-up is a sign of PD based on a new lesion.
- b. No FDG-PET at baseline and a positive FDG-PET at follow-up: If the positive FDG-PET at follow-up corresponds to a new site of disease confirmed by CT, this is PD. If the positive FDG-PET at follow-up is not confirmed as a new site of disease on CT, additional follow-up CT scans are needed to determine if there is truly progression occurring at that site (if so, the date of PD will be the date of the initial abnormal FDG-PET scan). If the positive FDG-PET at follow-up corresponds to a pre-existing site of disease on CT that is not progressing on the basis of the anatomic images, this is not PD.
- c. FDG-PET may be used to upgrade a response to a CR in a manner similar to a biopsy in cases where a residual radiographic abnormality is thought to represent fibrosis or scarring. The use of FDG-PET in this circumstance should be prospectively described in the protocol and supported by disease-specific medical literature for the indication. However, it must be acknowledged that both approaches may lead to false positive CR due to limitations of FDG-PET and biopsy resolution/sensitivity.

Note: A 'positive' FDG-PET scan lesion means one which is FDG avid with an uptake greater than twice that of the surrounding tissue on the attenuation corrected image.

Response Criteria

Evaluation of Target Lesions

Complete Response (CR): Disappearance of all target lesions. Any pathological lymph nodes (whether target or non-target) must have reduction in short axis to <10 mm.

Partial Response (PR): At least a 30% decrease in the sum of the diameters of target lesions, taking as reference the baseline sum diameters.

Progressive Disease (PD): At least a 20% increase in the sum of the diameters of target lesions, taking as reference the smallest sum on study (this includes the baseline sum if that is the smallest on study). In addition to the relative increase of 20%, the sum must also demonstrate an absolute increase of at least 5 mm. (Note: the appearance of one or more new lesions is also considered progressions).

Stable Disease (SD): Neither sufficient shrinkage to qualify for PR nor sufficient increase to qualify for PD, taking as reference the smallest sum diameters while on study.

Evaluation of Non-Target Lesions

Complete Response (CR): Disappearance of all non-target lesions and normalization of tumor marker level. All lymph nodes must be non-pathological in size (<10 mm short axis).

Note: If tumor markers are initially above the upper normal limit, they must normalize for a patient to be considered in complete clinical response.

Non-CR/Non-PD: Persistence of one or more non-target lesion(s) and/or maintenance of tumor marker level above the normal limits.

Progressive Disease (PD): Appearance of one or more new lesions and/or unequivocal progression of existing non-target lesions. Unequivocal progression should not normally trump target lesion status. It must be representative of overall disease status change, not a single lesion increase.

Although a clear progression of "non-target" lesions only is exceptional, the opinion of the treating physician should prevail in such circumstances, and the progression status should be confirmed at a later time by the review panel (or Principal Investigator).

Evaluation of Best Overall Response

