	Chan	ce of e	scalatio	on, MT	D in pl	ace or (de-esca	lation		
pesc:	0.981	0.928	0.847	0.744	0.625	0.496	0.363	0.232	0.109	
pstay:	0.013	0.033	0.043	0.041	0.031	0.018	0.008	0.002	0.000	
pdesc:	0.006	0.039	0.110	0.215	0.344	0.486	0.629	0.766	0.891	
p(T>2)	: 0.100	0.200	0.300	0.400	0.500	0.600	0.700	0.800	0.900	
mtddes	c· 0 99	0 0 93	6 0 82	8 0 67	6 0 50	0 0 32	4 0 1 7	2 0.06	4 0.010)

mtddesc: 0.990 0.936 0.828 0.676 0.500 0.324 0.172 0.064 0.010 Chance of MTD on de-escalation

The primary efficacy endpoint for Phase II is the rate of response by RECIST (CR, PR, SD, PD). The null hypothesis to be tested is that the RP2D observed in Phase I is not efficacious. We will use the standard Simon's two-stage design with 80% power at alpha level 0.05. The response rate is assumed to be 5% for the standard treatment and 20% for quinacrine in combination with capecitabine. The Phase II portion will first enroll 10 patients. The trial will be stopped if no patient responds to treatment. Otherwise, 19 additional patients will be enrolled for a total of 29 patients. The drug will be declared to have sufficient response rate if 4 or more subjects respond to treatment.

The other primary end point for Phase II is time to tumor progression, which will be analyzed by the Kaplan and Meier method.

Toxicity endpoint: If ever 5 of the initial cohort of 10 patients experience DLTs, or if ever 8 of the 29 total evaluable phase II patients do, the trial will be halted for excess toxicity and either dose adjusted or terminated. If the true chance of DLT is 33.3% the trial will be halted in this way with power 80.5%. If the true toxicity is at most 15%, the chance of termination in error is at most 6.3%.

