11.2 Sample Size/Accrual Rate

Sample size for Simon's two-stage Optimum design will be as large as 29 (if the study progresses to stage 2) as described in section 12.1. If the study requires a dose reduction after the first 6 patients have enrolled, the sample size may be as large as 35 (29 at a 100 mg daily dose of quinacrine plus 6 patients who were treated at a 100mg bid dose of quinacrine). The study is expected to accrue over two years.

Patient Replacement: If during the Phase I or phase II portion of the study a patient is lost to follow-up before the patient can be evaluated at least once clinically or radiologically, the patient will not be

evaluable for the primary endpoint and will be replaced. Patients that are taken off-treatment due to severe drug related toxicity will not be replaced. If a patient is lost to follow-up after at least one evaluation is completed the patient will not be replaced and will be considered a failure towards the primary endpoint.

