11.4 Analysis of Primary Endpoints

The intent-to-treat population will include all patients who have received at least one dose of both Capecitabine and quinacrine. The response rate and its 95% confidence interval will be estimated using the approach described by Koyama and Chen (71), which accounts for the interim futility analysis.

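### Sections 10, 11.2 and 11.4 give three unreconciled rules for who counts in the Phase II response rate, and using the Section 10 set would bias the reported rate upward

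*Combined protocol and SAP*

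**What the plan says.** Three places in the combined protocol and SAP bear on who is counted for the Phase II response endpoint.

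- **Section 10, Definitions.** Only patients with measurable disease at baseline who "have received at least one cycle of therapy, and have had their disease re-evaluated will be considered evaluable for response". A note adds patients with objective progression before the end of cycle 1. Re-evaluation is planned after every 3 cycles of 21 days, so the first planned scan falls at about week 9.
- **Section 11.4, Analysis of Primary Endpoints.** "The intent-to-treat population will include all patients who have received at least one dose of both Capecitabine and quinacrine". The next sentence says that the response rate and its 95% interval follow Koyama and Chen. It does not say that the intent-to-treat set is the denominator, or how a patient without a tumor assessment is scored.
- **Section 11.2, Patient Replacement.** A patient lost before any clinical or radiological evaluation is not evaluable for the primary endpoint and is replaced. A patient lost after at least one evaluation counts as a failure and is not replaced. "Patients that are taken off-treatment due to severe drug related toxicity will not be replaced".

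Section 11.1 sets the decision rule. "We will use the standard Simon's two-stage design with 80% power at alpha level 0.05", with 5% against 20%. Stage 1 takes 10 patients, and accrual ends there if none of them responds. If at least one does, "19 additional patients will be enrolled for a total of 29 patients", and success needs 4 or more responders.

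**The concern.** A patient with no tumor re-evaluation cannot have a documented response. Excluding such patients therefore removes only non-responders, and the reported rate can only go up, for reasons unrelated to the drug.

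These patients are foreseeable. Section 4.1 admits ECOG 2 and a life expectancy just over 3 months, while the first planned scan is at about week 9. Section 5.1 takes patients off therapy for grade 4 toxicity. Section 10 itself anticipates symptomatic deterioration without objective progression.

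With the denominator left open, the choice could be made after the responses are known. In a single-arm trial of at most 29 patients judged against a 5% reference, a few patients visibly move the headline figure.

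**Working it through.** **1. How the three rules treat the same patient** (each has received both drugs)

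| Patient | Section 10 | Section 11.2 | Section 11.4 set |
|---|---|---|---|
| Objective progression in cycle 1 | In | Not addressed | In |
| Stops in cycle 1 for severe drug toxicity, never re-evaluated | Out | Not replaced | In |
| Lost before any clinical or radiological evaluation | Out | Not evaluable, replaced | In |
| Examined at a cycle visit, lost before any scan | Out, unless that exam is a disease re-evaluation | Failure, not replaced | In |
| Dies or withdraws before any re-evaluation | Out | Not addressed, unless it is a loss to follow-up | In |

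Only the first row raises no conflict.

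**2. Reproducing the design in 11.1**

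Inputs: n1 = 10, stop if 0 respond; n2 = 19; success if the total is at least 4; p0 = 0.05, p1 = 0.20. With X1 ~ Bin(10, p) and X2 ~ Bin(19, p):

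P(success) = Σ over x = 1 to 10 of P(X1 = x) × P(X2 ≥ 4 − x)

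- p = 0.05: 0.3151 × 0.0665 + 0.0746 × 0.2453 + 0.0105 × 0.6226 + P(X1 ≥ 4) = 0.0210 + 0.0183 + 0.0065 + 0.0010 = **0.0468**.
- p = 0.20: 0.2048 + 0.2770 + 0.1984 + 0.1209 = **0.801**.

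The stated alpha of 0.05 and power of 80% reproduce. They also hold with all treated patients counted and unassessed patients scored as non-responders.

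**3. Unassessed patients dropped, not refilled**

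Treat 29 and drop k who were never re-evaluated. The responder count is unchanged, so the stage 1 rule and the cut-off of 4 give the same decision and type I error stays at 0.0468. Only the reported proportion moves. With 4 responders:

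- k = 0: 4/29 = 13.8%
- k = 3: 4/26 = 15.4%
- k = 6: 4/23 = 17.4%

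The interval shifts with the proportion, and the patient numbers behind it are no longer the planned 10 and 19.

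**4. Unassessed patients refilled to 29 evaluable**

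Let f be the share of treated patients who are non-evaluable, all non-responders. An all-treated rate of 5% becomes 0.05/(1 − f) among evaluable patients. Putting that into the formula in step 2:

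| f (assumed) | Rate among evaluable | Type I error against 5% of all treated |
|---|---|---|
| 0 | 5.0% | 4.7% |
| 5% | 5.3% | 5.5% |
| 10% | 5.6% | 6.4% |
| 20% | 6.25% | 9.0% |
| 30% | 7.1% | 12.9% |

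The documents give no non-evaluable share, so k and f are assumptions.

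**The case against.** The best defence is that 11.4 already answers the question. It is headed as the analysis of primary endpoints, defines the all-treated set, and goes straight on to estimating the response rate. Section 10 describes how response is measured and names no primary analysis set. That is the more natural reading, and under it there is no inflation. It does not settle the matter, because 11.2, in the same statistical section, calls some treated patients not evaluable for the primary endpoint and replaces them. No sentence says how an unassessed patient is scored.

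Two stronger readings are tempting, and the documents do not support either.

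- A reader might infer that the test against 5% has an inflated false-positive rate. The rule counts responders, and removing non-responders cannot produce a fourth one. Inflation needs refilling to 29 evaluable patients. Section 11.2 orders replacement only for patients lost before any evaluation, rules it out for severe drug toxicity, and is silent on deaths and other withdrawals.
- A reader might infer that early failures in general leave the denominator. Objective progressors in cycle 1 stay in by the note. Later progressors found before week 9 have received a cycle and been re-evaluated, so they stay too. The condition is that a cycle was received. Section 3.6 continues tumor measurements every 6 to 9 weeks after treatment stops, so a patient who stops for toxicity after one cycle is still due a scan. Section 10 also asks for every effort to document progression after symptomatic deterioration.

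The excluded group is therefore limited to treated patients who die, deteriorate, withdraw or stop in cycle 1 without any re-evaluation.

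**Conclusion.** The conflict is real and should be resolved before analysis. Its consequence is conditional: if Section 10 rather than 11.4 supplies the denominator, the reported response rate and its interval are too high, by 1.6 percentage points (13.8% to 15.4%) with 3 of 29 dropped and 3.6 points (to 17.4%) with 6 dropped, at 4 responders.

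The go/no-go decision keeps its 4.7% type I error unless patients are refilled. With full refilling, a 5% non-evaluable share already takes it past the stated 0.05, to 5.5%. The current replacement rule would refill only part of the excluded group, so the figures in step 4 show what complete refilling would do and do not predict what this plan would do.

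The conclusion assumes that patients who were never re-evaluated are non-responders, which follows from how response is defined. The numbers dropped are illustrative.

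**What to change.** - In Sections 10 and 11.4, state that the primary response rate, its Koyama-Chen interval, the 0/10 futility count and the 4/29 success count all use every Phase II patient who received at least one dose of both drugs. Any patient without a post-baseline tumor evaluation counts as a non-responder.
- In Section 11.2, align the Phase II replacement rule with this, so that a patient who received both drugs stays in the 29 and is not exchanged for an evaluable one.
- Keep the Section 10 evaluable set for a labelled supportive analysis only.

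The cost is wording and possibly a slightly lower headline response rate. No patients or procedures are added, and the design keeps its computed alpha of 0.0468 and power of 0.801.
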